8.2.5.1.2 Overall Survival (OS)

The nonparametric Kaplan-Meier method will be used to estimate the survival curves. The treatment difference in survival will be assessed by the stratified log-rank test. A stratified Cox proportional hazard model with Efron's method of tie handling will be used to assess the magnitude of the treatment difference (i.e., the hazard ratio). The hazard ratio and its 95% CI from the stratified Cox model with a single treatment covariate will be reported. The same stratification factors used for randomization (see Section 5.4) will be used as the stratification factors in both the stratified log-rank test and the stratified Cox model for the analyses in all subjects and in subjects with PD-L1 CPS 1. For analyses in the PD-L1 CPS 20 subgroup, HPV status and ECOG status will be used as the stratification factors. In the event that there are low event counts (<5) in one or more strata, for the analysis purpose, strata will be combined to ensure sufficient number of events in each stratum. The order of stratification factors to combine strata over is the same as specified for PFS analysis.

Since subjects in the standard therapy arm are expected to discontinue treatment earlier compared to subjects in the pembrolizumab arms, and they may switch to another anti-PD-1 treatment following confirmation of progressive disease, adjustment for the effect of crossover on OS may be performed based on recognized methods, e.g. the Rank Preserving Structural Failure Time model proposed by Robins and Tsiatis (1989) [55], two stage model, etc., based

on an examination of the appropriateness of the data to the assumptions required by the methods.

8.2.5.1.3 Proportion Progression Free at 6 Months and 12 Months

Kaplan-Meier estimates of the survival function for PFS at 6 months and 12 months will be provided by treatment group. Confidence intervals for the difference between the treatment groups (pembrolizumab vs. standard treatment or a combination of pembrolizumab with chemotherapy vs. standard treatment) will be constructed using standard methods.

8.2.5.1.4 Objective Response Rate (ORR)

The stratified Miettinen and Nurminen's method will be used for comparison of the objective response rates between the treatment groups. The difference in ORR and its 95% CI from the stratified Miettinen and Nurminen method with strata weighting by sample size will be provided. The same stratification factors used for randomization (see Section 5.4) will be used as the stratification factors in the analysis of all subjects and subjects with PD-L1 CPS 1. For analyses in the PD-L1 CPS 20 subgroup, HPV status and ECOG status will be used as the stratification factors. In the event that there are low responses (<5) in one or more strata, for the analysis purpose, strata will be combined to ensure sufficient number of responses in each stratum. The order of stratification factors to combine strata over is the same as specified for PFS analysis. Sensitivity analyses will be performed for comparison of ORR based on investigator's assessment.

8.2.5.1.5 Duration of Response (DOR)

For subjects who demonstrate CR or PR, DOR is defined as the time from first documented evidence of CR or PR until disease progression or death due to any cause, whichever occurs first. Censoring rules for DOR are summarized in [Table 19](#). DOR will be assessed using RECIST 1.1 separately by BICR and by investigator's assessment.

For each DOR analysis, a corresponding summary of the reasons responding subjects are censored will also be provided. Subjects who are alive, have not progressed, have not initiated new anticancer treatment, have not been determined to be lost to follow-up, and have had a disease assessment within ~5 months of the data cutoff date are considered ongoing responders at the time of analysis. If a subject meets multiple criteria for censoring, the censoring criterion that occurs earliest will be applied.

Table 19 Censoring Rules for DOR

Situation	Date of Progression or Censoring	Outcome
No progression nor death, no new anticancer therapy initiated	Last adequate disease assessment	Censor (nonevent)
No progression nor death, new anticancer therapy initiated	Last adequate disease assessment before new anticancer therapy initiated	Censor (nonevent)
Death or progression after ≥ 2 consecutive missed disease assessments	Last adequate disease assessment prior to the ≥ 2 missed adequate disease assessments	Censor (nonevent)

Situation	Date of Progression or Censoring	Outcome
Death or progression after \leq 1 missed adequate disease assessments	PD or death	End of response (Event)
A missed disease assessment includes any assessment that is not obtained or is considered inadequate for evaluation of response.		

8.2.5.1.6 Summary of Efficacy Analysis Methods

A summary of the primary analysis strategy for the primary and secondary efficacy endpoints is provided in [Table 20](#).

Table 20 Efficacy Analysis Methods for Primary and Secondary Efficacy Endpoints

Endpoint/Variable (Description, Time Point)	Statistical Method	Analysis Population	Missing Data Approach
Primary Analyses:			
PFS (RECIST 1.1) by BICR	Testing: Stratified Log-rank test Estimation: Stratified Cox model with Efron's tie handling method	ITT 
• All subjects• Subjects with PD-L1 CPS 20 and CPS 1	Censored according to rules in Table 18
OS	Testing: Stratified Log-rank test (for superiority hypotheses only) Estimation: Stratified Cox model with Efron's tie handling method	ITT 
• All subjects• Subjects with PD-L1 CPS 20 and CPS 1	Censored at last known alive date
Secondary Analyses:			
PFS at 6 months/12 months (RECIST 1.1) by BICR	Kaplan-Meier estimation with CI	ITT 
• All subjects• Subjects with PD-L1 CPS 20 and CPS 1	Censored according to primary censoring rule in Table 18
ORR (RECIST 1.1) by BICR	Stratified Miettinen and Nurminen method	ITT 
• All subjects• Subjects with PD-L1 CPS 20 and CPS 1	Subjects with missing data are considered nonresponders
Exploratory Analyses:			
DOR (RECIST 1.1) by BICR	Summary statistics using Kaplan-Meier method	All responders in ITT	Nonresponders are excluded in analysis
Sensitivity analyses will be performed for PFS, ORR and DOR based on investigator's assessment.			

8.2.5.2 Statistical Methods for Safety Analyses

Safety and tolerability will be assessed by clinical review of all relevant parameters including AEs, laboratory tests, vital signs, and ECG measurements.

The analysis of safety results will follow a tiered approach (Table 21). The tiers differ with respect to the analyses that will be performed. Safety parameters or adverse experiences of special interest that are identified *a priori* constitute "Tier 1" safety endpoints that will be subject to inferential testing for statistical significance with p-values and 95% confidence intervals provided for between-group comparisons. Other safety parameters will be considered Tier 2 or Tier 3. Tier 2 parameters will be assessed via point estimates with 95% confidence intervals provided for between-group comparisons; only point estimates by treatment group are provided for Tier 3 safety parameters.

Adverse experiences (specific terms as well as system organ class terms) and predefined limits of change in laboratory, vital signs, and ECG parameters that are not pre-specified as Tier-1 endpoints will be classified as belonging to "Tier 2" or "Tier 3," based on the number of events observed. Membership in Tier 2 requires that at least 4 subjects in any treatment group exhibit the event; all other adverse experiences and predefined limits of change will belong to Tier 3.

The threshold of at least 4 events was chosen because the 95% confidence interval for the between-group difference in percent incidence will always include zero when treatment groups of equal size each have less than 4 events and thus would add little to the interpretation of potentially meaningful differences. Because many 95% confidence intervals may be provided without adjustment for multiplicity, the confidence intervals should be regarded as a helpful descriptive measure to be used in review, not a formal method for assessing the statistical significance of the between-group differences in adverse experiences and predefined limits of change.

Continuous measures such as changes from baseline in laboratory, vital signs, and ECG parameters that are not pre-specified as Tier-1 endpoints will be considered Tier 3 safety parameters. Summary statistics for baseline, on-treatment, and change from baseline values will be provided by treatment group in table format.

For this protocol, there are no Tier 1 events. Adverse experiences (specific terms as well as system organ class terms), consisting of the percentage of subjects with any AE, any drug-related AE, any Grade 3-5 AE, any serious AE, any AE which is both drug-related and Grade 3-5, any AE which is both serious and drug-related, dose modification due to AE, and who discontinued due to an AE, and death that are not pre-specified as Tier-1 endpoints will be classified as belonging to "Tier 2" or "Tier 3," based on the number of events observed. Membership in Tier 2 requires that at least 4 subjects in any treatment group exhibit the event; all other adverse experiences will belong to Tier 3.

Table 21 Analysis Strategy for Safety Parameters

Safety Tier	Safety Endpoint	p-Value	95% CI for Treatment Comparison	Descriptive Statistics
Tier 2	Any AE		X	X
	Any Grade 3-5 AE		X	X
	Any Serious AE		X	X
	Any Drug-Related AE		X	X
	Any Serious and Drug-Related AE		X	X
	Any Grade 3-5 and Drug-Related AE		X	X
	Dose Modification due to AE		X	X
	Discontinuation due to AE		X	X
	Death		X	X
	Specific AEs, SOCs (including ≥ 4 of subjects in one of the treatment groups)		X	X
Tier 3	Specific AEs, SOCs (incidence < 4 of subjects in all of the treatment groups)			X
	Change from Baseline Results (Labs, ECGs, Vital Signs)			X

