		1	2	3	4	To be repeated beyond 6 cycles	5	6	Discontinuation	Safety Follow-up	Follow-Up Visits ^b	Survival Follow-up ^c
Scheduling Window (Days) ^d :	Screening (Visit 1)	-28 to -1	+5 ^d	± 3	± 3	± 3	± 3	± 3	At time of treatment discon	30 days after last dose of study medication (± 3 days)	Every 6 weeks post discon or per footnote	Every 12 weeks (± 14 days)
Blood for Genetics ^{r,y}		X										
Correlative Blood Samples for DNA ^s		X	X	X					X			
Correlative Blood Samples for RNA ^s		X	X	X					X			
Correlative Blood Samples for plasma ^s		X										
Correlative Blood Samples for serum ^s		X										
Efficacy Measurements												
Tumor Imaging and RECIST Assessment	X ^t				X ^u		X ^u	X ^{b,v}		X ^b		
Tumor Tissue Collection												
Archival or Newly Obtained Tissue Collection for Subjects with Oropharynx Cancer Tested Locally for HPV Status for Stratification (newly obtained may be obtained 90 days prior to treatment initiation)	X ^w											
Newly Obtained Tissue Collection for Biomarker Analysis (Tested Centrally) on All Subjects Prior to Randomization for Stratification (may be obtained 90 days prior to treatment initiation). Tissue sample for FBR.	X ^w											
Patient-Reported Outcomes												
EuroQol EQ-5D ^x		X	X	X	X ^j		X ^j	X	X ^x			
EORTC QLQ-C30 ^x		X	X	X	X ^j		X ^j	X	X ^x			

Trial Period:	Screening Phase	Treatment Cycles (3-Week Cycles) ^a						End of Treatment	Posttreatment		
		1	2	3	4	To be repeated beyond 6 cycles	5	6	Safety Follow-up	Follow-Up Visits ^b	Survival Follow-up ^c
Treatment Cycle/Title:	Screening (Visit 1)								Discontinuation		
Scheduling Window (Days) ^d :		-28 to -1	+5 ^d	± 3	± 3	± 3	± 3	± 3	At time of treatment discon	30 days after last dose of study medication (± 3 days)	Every 6 weeks post discon or per footnote
EORTC QLQ-H&N 35 ^x			X	X	X	X ^j		X ^j	X	X ^x	
Pain Medication Log ^x		X	X	X	X	X	X	X	X	X	

- a. In general, assessments/procedures are to be performed on Day 1 and prior to the first dose of treatment for each cycle unless otherwise specified. Treatment cycles are 3 weeks. For subjects in the pembrolizumab plus chemotherapy arm, subjects may receive a maximum of 6 cycles (infusions) of platinum and 5-FU. Pembrolizumab treatment may continue after discontinuation of chemotherapy. Imaging should be performed at 9 weeks after randomization and every 6 weeks thereafter (42 days ±7 days) regardless of any treatment delays.

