- h. AEs and laboratory safety measurements will be graded per NCI CTCAE version 4.0. All AEs, whether gradable by CTCAE or not, will also be evaluated for seriousness.
- i. Record all AEs occurring within 30 days after the last dose of trial treatment. Report all SAEs (related and unrelated to trial treatment) and ECIs occurring up until 90 days following cessation of treatment, or 30 days following cessation of treatment if the subject initiates new anticancer therapy, whichever comes first. Afterwards, report only SAEs and ECIs that are related to trial treatment.
- j. To be repeated every 2 cycles after Cycle 4. ePROs will continue up to 1 year.
- k. Vital signs to include temperature, pulse, respiratory rate, weight and blood pressure. Height will be measured at Visit 1 only.

- l. For women of reproductive potential, a serum pregnancy test should be performed within 72 hours prior to first dose of trial treatment. A urine test can be considered if serum is not appropriate. Pregnancy tests (serum and/or urine tests) should be repeated if required by local guidelines.
- m. Coagulation factors (PT/INR and aPTT) should be tested as part of the screening procedures for all subjects. PTT may be performed if the local lab is unable to perform aPTT. Any subject receiving anticoagulant therapy should have coagulation factors monitored closely throughout the trial.
- n. ECOG and laboratory tests for screening are to be performed within 10 days prior to the first dose of trial treatment. Screening labs must be collected and assessed prior to randomizing the subject. ECOG must be 0 or 1 on the first day of dosing. See Section 7.1.3 for details regarding laboratory tests.
- o. After Cycle 1, lab samples can be collected up to 72 hours prior to the scheduled time point. See Section 7.1.3 for details regarding laboratory tests. T3 or FT3 can be assayed based on local standards.
- p. Unresolved abnormal labs that are drug-related AEs should be followed until resolution. Labs do not need to be repeated after the end of treatment if labs are within normal range.

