Newly Obtained Tissue Collection for Biomarker Analysis (tested centrally) On all Subjects Prior to Randomization for Stratification (may be obtained 90 days prior to treatment initiation) ^u . Tissue sample for FBR.	X ^u																			
Patient-Reported Outcomes (ePROs)																				
EuroQol EQ-5D	X ^v		X ^v		X ^v		X ^v		X ^{j,v}		X ^{j,v}		X ^{j,v}		X ^v	X ^v				
EORTC QLQ-C30	X ^v		X ^v		X ^v		X ^v		X ^{j,v}		X ^{j,v}		X ^{j,v}		X ^v	X ^v				
EORTC QLQ-H&N 35	X ^v		X ^v		X ^v		X ^v		X ^{j,v}		X ^{j,v}		X ^{j,v}		X ^v	X ^v				
Pain Medication Log ^v	X	X	X	X	X	X	X	X	X	X	X	X	X	X	X	X	X	X		

- a. In general, assessments/procedures are to be performed prior to the treatment dose. Carboplatin and cisplatin will be dosed on Day 1 of each 3-week cycle. 5-FU will be dosed continuously on Days 1-4 of each 3-week cycle. Subjects may receive a maximum of 6 cycles of platinum and 5-FU. Cetuximab will be dosed on Days 1, 8 and 15 of each 3-week cycle. After discontinuing chemotherapy, cetuximab treatment may continue until disease progression or unacceptable toxicity occurs. Imaging should be performed at 9 weeks after randomization and every 6 weeks thereafter (42 days \pm 7 days) regardless of any treatment delays.
- b. In subjects who discontinue study therapy without documented disease progression, every effort should be made to continue monitoring their disease status by radiologic imaging every 6 weeks (\pm 7 days) (or every 9 weeks \pm 7 days after the first year) until (1) the start of new anticancer treatment, (2) disease progression as assessed by the central imaging vendor, (3) death, or (4) the end of the study, whichever occurs first. The first follow-up imaging assessment should occur 6 weeks (\pm 7 days) from the last scheduled on-treatment imaging timepoint (or 9 weeks \pm 7 days from the last scheduled on-treatment imaging timepoint after the first year).

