- k. Vital signs to include temperature, pulse, respiratory rate, weight and blood pressure. Height will be measured at Visit 1 only.
- l. For women of reproductive potential, a serum pregnancy test should be performed within 72 hours prior to first dose of trial treatment. A urine test can be considered if serum is not appropriate. Pregnancy tests (serum and/or urine tests) should be repeated if required by local guidelines.
- m. Coagulation factors (PT/INR and aPTT) should be tested as part of the screening procedures for all subjects. PTT may be performed if the local lab is unable to perform aPTT. Any subject receiving anticoagulant therapy should have coagulation factors monitored closely throughout the trial.
- n. ECOG and laboratory tests for screening are to be performed within 10 days prior to the first dose of trial treatment. Screening labs must be collected and assessed prior to randomizing the subject. ECOG must be 0 or 1 on the first day of dosing. See Section 7.1.3 for details regarding laboratory tests.
- o. After screening, labs should be taken on day of treatment or labs may be drawn up to 72 hours prior to dosing if acceptable per local standard of care. See Section 7.1.3 for details regarding laboratory tests. T3 or FT3 can be assayed based on local standards.
- p. Unresolved abnormal labs that are drug-related AEs should be followed until resolution. Labs do not need to be repeated after the end of treatment if labs are within normal range.
- q. See Section 7.1.2.7 correlative blood sample information. Detailed instructions with specific timepoints per sample are provided in the Procedures Manual.
- r. The initial tumor imaging will be performed within 28 days prior to randomization. Scans performed as part of routine clinical management are acceptable for use as the screening scan if they are of diagnostic quality and performed within 28 days prior to randomization. Local reading (investigator assessment with site radiology reading) will be used to determine eligibility and for subject management. The Sponsor will collect radiological assessments for analysis by a central imaging vendor. The processes for image collection and transmission to the central vendor are in the Site Imaging Manual.

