7.1.3.1 Laboratory Safety Evaluations (Hematology, Chemistry and Urinalysis)

Laboratory tests for hematology, chemistry and urinalysis are specified in [Table 14](#).

Table 14 Laboratory Tests

Hematology	Chemistry	Urinalysis	Other
Hematocrit	Albumin	Blood	Serum human chorionic gonadotropin ^a
Hemoglobin	Alkaline phosphatase	Glucose	PT (INR)
Platelet count	Alanine aminotransferase (ALT)	Protein	aPTT ^c
WBC (total and differential)	Aspartate aminotransferase (AST)	Specific gravity	Total triiodothyronine (T3) or Free T3 ^b
Red Blood Cell Count		Microscopic exam, if abnormal results are noted	Free thyroxine (T4)
Absolute Neutrophil Count	Calcium ^c	Urine pregnancy test ^a	Thyroid-stimulating hormone (TSH)
Absolute Lymphocyte Count	Chloride		Blood for correlative studies
	Creatinine		PK (for subjects on the pembrolizumab arms)
	Glucose		Anti-pembrolizumab Antibodies (for subjects on the pembrolizumab arms)
	Magnesium		
	Phosphorus		
	Potassium		
	Sodium		
	Total Bilirubin		
	Direct Bilirubin, if total bilirubin is elevated above the upper limit of normal		
	Total protein		
	Blood Urea Nitrogen		
	A measure of carbon dioxide (CO ₂ or bicarbonate) ^b		

Hematology	Chemistry	Urinalysis	Other
	Uric acid		
	Urea ^d		

a. Perform on women of childbearing potential only. Serum pregnancy test is preferred but urine test can be considered if serum not appropriate.
b. If available as standard of care in your region. The carbon dioxide may be either a measurement of CO₂ or bicarbonate as an electrolyte.
c. Corrected calcium should be checked for subjects with hypoalbuminemia.
d. Blood Urea Nitrogen is preferred; if not available urea may be tested.
e. PTT may be performed if the local lab is unable to perform aPTT.

Laboratory tests for screening should be performed within 10 days prior to the first dose of trial treatment. Screening labs should be collected and assessed prior to randomizing the subject. After Cycle 1, predose laboratory procedures can be conducted up to 72 hours prior to dosing. Results must be reviewed by the investigator or qualified designee and found to be acceptable prior to each dose of trial treatment.

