8.2.4.2 Safety Analysis Populations

The All-Subjects-as-Treated (ASaT) population will be used for the analysis of safety data in this study. The ASaT population consists of all randomized subjects who received at least one dose of study treatment. Subjects will be included in the treatment group corresponding to the study treatment they actually received for the analysis of safety data using the ASaT population. For most subjects this will be the treatment group to which they are randomized. Subjects who take incorrect study treatment for the entire treatment period will be included in the treatment group corresponding to the study treatment actually received. Any subject who receives the incorrect study medication for one cycle but receives the correct treatment for all other cycles will be analyzed according to the correct treatment group and a narrative will be provided for any events that occur during the cycle for which the subject is incorrectly dosed.

At least one laboratory or vital sign measurement obtained subsequent to at least one dose of study treatment is required for inclusion in the analysis of each specific parameter. To assess change from baseline, a baseline measurement is also required.

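### Blood counts and chemistry are scheduled weekly in control but once per cycle with pembrolizumab plus chemotherapy, and the safety plan neither matches the draws nor notes the difference

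*Combined protocol and SAP*

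**What the plan says.** **Control schedule.** In the Section 6.1.2 flow chart the CBC and chemistry rows are marked in every Day 1, 8 and 15 column. The footnotes agree: "Cetuximab will be dosed on Days 1, 8 and 15 of each 3-week cycle", and "After screening, labs should be taken on day of treatment or labs may be drawn up to 72 hours prior to dosing". Section 7.1.3.1 adds: "Results must be reviewed by the investigator or qualified designee and found to be acceptable prior to each dose of trial treatment". For cetuximab that means every week.

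**Pembrolizumab plus chemotherapy schedule.** The Section 6.1.1 chart has no Day 8 or Day 15 columns. Its general rule is that "assessments/procedures are to be performed on Day 1 and prior to the first dose of treatment for each cycle unless otherwise specified". CBC and chemistry are marked at screening, not in Cycle 1, and then once per cycle from Cycle 2. The laboratory footnote gives only a window: "After Cycle 1, lab samples can be collected up to 72 hours prior to the scheduled time point".

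**Chemotherapy.** Section 5.3 gives both arms the same platinum and 5-FU regimen, and Section 5.2 caps it at six cycles.

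**Safety analysis.** Section 8.2.5.2 makes "predefined limits of change in laboratory, vital signs, and ECG parameters that are not pre-specified as Tier-1 endpoints" eligible for Tier 2 once four subjects in any arm have the event. Section 8.2.4.2 sets a low bar for entering a laboratory analysis: "At least one laboratory or vital sign measurement obtained subsequent to at least one dose of study treatment is required for inclusion". The one interpretive caution in Section 8.2.5.2 concerns multiplicity. It also states: "For this protocol, there are no Tier 1 events".

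**The concern.** The number of scheduled looks at the same chemotherapy differs about threefold between the two arms, and nothing in the analysis accounts for it. A count that falls and recovers between Day 1 draws can be recorded in control and missed in the combination arm.

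There are two routes into the results. One is the laboratory-limit wording quoted above. The other is adverse event reporting: Section 7.2 allows an abnormal laboratory finding to be an adverse event, so asymptomatic cytopenias can enter the rows of Table 21 for specific AEs, any Grade 3-5 AE and dose modification due to AE.

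Safety and tolerability is a secondary objective (Section 3.2). Section 4.3 names neutropenia, anemia and thrombocytopenia among the comparator's Grade 3-4 burden and gives a tolerability advantage of pembrolizumab as a reason for the trial. Without a caveat, a reader could take a lower cytopenia rate as less myelosuppression when part of it is sampling frequency.

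**Working it through.** **1. Scheduled post-baseline draws, Cycle 1 Day 8 to Cycle 7 Day 1**

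- Control: 2 (Cycle 1) + 5 × 3 (Cycles 2 to 6) + 1 (Cycle 7 Day 1) = 18.
- Combination: Day 1 of Cycles 2 to 7 = 6.
- Stopping at the end of Cycle 6 gives 17 against 5.

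The ratio is 3.0 to 3.4. The filled control rows are unlikely to be an artifact of the text extraction, because ECOG status in the same chart is marked only once per cycle.

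**2. Illustration of what this can do**

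The documents give no nadir timing, episode length, recurrence rate or rate of unscheduled draws, so all of these are assumed. Inputs:

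- 825/3 = 275 subjects per arm.
- A true Grade 3-4 rate of 22% in *both* arms. Section 4.3 cites 22% for neutropenia, but as an adverse event rate, so its use as a true laboratory rate is an assumption.
- Each affected subject has k episodes of d days, in different cycles, with uniform onset.

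Detected rates:

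- Control: 0.22 × [1 − (1 − min(1, d/7))^k]
- Combination: 0.22 × [1 − (1 − d/21)^k]
- SE = √(p₁q₁/275 + p₂q₂/275)

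Example, d = 7 and k = 1: 22.0% against 0.22 × 7/21 = 7.3%, a gap of 14.7 points.

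Gap in percentage points, control minus combination (95% CI), scheduled draws only:

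| Episode length | k = 1 | k = 3 | k = 6 |
|---|---|---|---|
| 3 days | 6.3 (2.3, 10.3) | 9.7 (4.2, 15.3) | 8.0 (1.7, 14.2) |
| 7 days | 14.7 (8.9, 20.5) | 6.5 (0.02, 13.0) | 1.9 (−4.9, 8.7) |
| 14 days | 7.3 (0.9, 13.8) | 0.8 (−6.1, 7.7) | 0.0 (−6.9, 7.0) |

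The true difference is zero throughout, yet six of nine intervals exclude it. If unscheduled draws catch half of the missed subjects in each arm, the gaps fall to between 0.0 and 7.3 points and one interval of nine excludes zero (d = 7, k = 1: 0.9 to 13.8).

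**3. Is a Day 1-only comparison clean?**

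Not fully. Detected toxicity can lead to a dose reduction, which is not reversed (Section 5.2.1.2), or to G-CSF (Tables 6 and 8). Weekly monitoring can therefore lower later risk in control. This was simulated with 600,000 affected subjects per arm and six cycles. Each cycle has at most one episode, with the stated starting probability, and each detected episode halves later risk, at most twice. Detected rates in %, gaps in points:

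| Scenario | Control, all draws | Control, Day 1 | Combination | All-draws gap | Matched gap |
|---|---|---|---|---|---|
| 7 days, every cycle | 22.0 | 14.3 | 20.1 | +1.9 | −5.8 |
| 7 days, 50% per cycle | 21.7 | 11.0 | 14.6 | +7.0 | −3.7 |
| 3 days, every cycle | 21.2 | 10.2 | 13.3 | +8.0 | −3.1 |
| 14 days, every cycle | 22.0 | 20.4 | 22.0 | 0.0 | −1.6 |

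If a reduction cuts risk by only 20%, the matched gaps are −2.1, −1.5, −1.3 and −0.3.

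**4. Cycle 2 Day 1 alone**

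This draw precedes any platinum or 5-FU reduction, so dose feedback cannot act on it. With an episode in every cycle, the expected rate is 0.22 × d/21 in both arms: 3.1% for 3 days, 7.3% for 7 days and 14.7% for 14 days. The arms are equal, apart from any difference in Cycle 1 G-CSF use, but events are fewer.

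**The case against.** The strongest reply is that the laboratory-limit sentence is framework text. Every Tier 2 row of Table 21 is an adverse event category or death. The only laboratory row is change from baseline, in Tier 3, with no between-arm interval. A reader might infer that the plan commits to a between-arm comparison of laboratory limits or worst grades; Table 21 does not support that. What stands against the plan is that the text leaves such a comparison open and the adverse event rows carry the same asymmetry.

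Second, a laboratory table cannot rematch adverse events that investigators have already reported. That is correct: only a footnote reaches those rows.

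Third, a matched table can mislead too. In two of the four feedback scenarios above (7-day and 14-day episodes in every cycle) the all-cycle matched gap lies further from the true zero than the all-draws gap. This also stands. It is why Cycle 2 Day 1 should lead and the later rows need a label.

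Fourth, Section 7.1 allows unscheduled procedures, which shrink the gap by an unknown amount, and Section 8.2.5.2 already calls its intervals descriptive. Both are true and keep the point minor. Neither tells the reader that detection differs by arm. The supplemental SAP is not available, but Sections 8.0 and 8.2.5 send exploratory and PRO methods there, not the safety methods.

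**Conclusion.** The concern holds as a minor one. The unequal schedule follows directly from the flow charts and their footnotes, and the safety sections neither match draws nor mention it. The likely direction is more transient, asymptomatic laboratory abnormalities recorded in control.

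The size is not known and may be zero. The range of 0.0 to 14.7 points rests on assumed episode lengths, recurrence, uniform onset and a borrowed 22% rate. A reader might take the upper end as an estimate of bias; the documents give no basis for that. Nor do they support extending the point to efficacy, serious adverse events, febrile neutropenia or deaths, which do not depend on scheduled draws in this way. There are no Tier 1 safety tests to distort.

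**What to change.** Two additions to Section 8.2.5.2:

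1. **Supplementary table.** Wherever laboratory limits or worst grades are compared between pembrolizumab plus chemotherapy and standard treatment, keep the all-draws result and add a table limited to scheduled pre-cycle Day 1 draws during platinum/5-FU. Put Cycle 2 Day 1 in the lead row. Label the later-cycle rows as possibly leaning against the combination, through dose reductions or G-CSF prompted by weekly monitoring in control. Where control chemotherapy restarted on Day 8 or 15 (Section 5.2.1.2.4), use the draw three weeks after that infusion.
2. **Footnote.** State that the all-draws laboratory contrast, cytopenia adverse event rates and dose-modification rates may partly reflect more frequent scheduled draws in control.

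The table addresses laboratory values only; the footnote is what covers reported adverse events. The cost is some SAP wording and one extra descriptive table from data already collected. The drawback is that the cleanest row has few events (7.3% per arm instead of 22% under 7-day episodes in every cycle), and it does not remove differences in Cycle 1 G-CSF use.
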